PROTOCOL

Official Title: Deep brain stimulation effects on gait and balance in patients with Parkinson's disease

PI: [name] [name]

Document Date: January 4, 2016

NCT Number: NCT02022735

1. STUDY DESIGN AND SCHEMA:

Gait and balance problems are dopamine resistant features of Parkinson's disease (PD).

Deep brain stimulation of sub-thalamic nucleus (STN-DBS) is an established surgical method that improves motor symptoms and gait in PD, however it may produce unexpected freezing of gait and balance problems in some patients, presumably due to overstimulation and gait incoordination. The aim of this study is to identify the differential effects of unilateral STN stimulation versus bilateral stimulation on gait kinematics in patients with PD and associated gait dysfunction.

2. BACKGROUND AND RATIONALE :

Freezing of gait (FOG) and walking difficulties represent perhaps the most difficult challenges in the treatment of Parkinson's disease (PD). PD patients experience frequent difficulty initiating walking, shuffling and postural instability (Vu, Nutt et al. 2012). In spite of dopaminergic therapy, walking difficulties continue to progress and only rarely do non-dopaminergic treatments provide benefit. Deep brain stimulation of sub-thalamic nucleus (STN-DBS) improves motor scores, walking and FOG (St George, Nutt et al. 2010). In some patients, even after appropriate fine tuning of programming, walking and balance continue to be a problem. One explanation can be the progression of the disease, however in some cases the FOG appears soon after the DBS. This has been attributed to overstimulation and perhaps asymmetric stimulation in the networks involved in gait

control. Several studies have looked at the parameters of stimulation and have concluded that reducing the frequency of stimulation would ameliorate walking difficulties (Fasano, Herzog et al. 2011). Similarly, reducing the amplitude contralateral to the most affected side is associated with less FOG (Moreau, Defebvre et al. 2008).

A growing body of literature suggests that right-hemisphere circuitry seems to be more affected than the left in patients with FOG (Fling, Cohen et al. 2013) and that patients with worse symptoms on the left are more likely to develop postural instability gait dysfunction (PIGD) (Giladi, McDermott et al. 2001)

3. OBJECTIVES

In this study we aim to evaluate the effects of differential STN stimulation on walking. We hypothesize that in patients with FOG, unilateral stimulation on the most affected hemisphere will ameliorate walking in a higher degree than bilateral stimulation. Functional asymmetry of STN was shown before by other studies (Castrioto, Meaney et al. 2011) and is thought that unilateral STN stimulation has effects that are similar with bilateral STN on UPDRS motor scores, effect called dominant STN. Since the effects of unilateral stimulation on walking are not completely understood, we plan to determine if unilateral stimulation has differential effects on gait kinematics.

4. STUDY POPULATION

Inclusion criteria are: patients with idiopathic PD with Hoehn and Yahr Stage 1-3 that have undergone STN-DBS and had developed difficulty walking 6-12 months after the DBS on stable dosage dopamine agonist/levodopa, expected to remain on the same dosage of treatment for the next 3 months; age 45-70.

Exclusion criteria are: past medical history of seizures, renal insufficiency and history of cardiac arrhythmia, previous DBS, severe arthritis, women of childbearing potential, dementia and less than 45 and over 70 years old.

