5. MEASUREMENTS AND EVALUATION

This study is meant to see if there is improvement in gait or freezing of gait after changes in the stimulation parameters.

- In the first part of the study subjects (1 visit) will be randomly assigned to four different stimulation parameters: both stimulators ON, both stimulators off, right stimulator ON, left stimulator ON. We will assess participants' gait using clinical scales as well as wearable sensors attached to the body. Assessments will be done one hour after each change in the stimulation parameters.
- In the second part of the study that participants may be asked to participate in, changes in the frequency of stimulation and contact stimulation will be performed. Four different stimulation settings will be tested. In this part evaluations will be done.

PART 1

Screening: At this visit, the study investigator will discuss the details of the research study and the consent form with the study participant.

The following procedures will also be completed:

- Sign informed consent form.
- Collection of a complete medical history and a neurological exam.
- United Parkinson's disease rating scale (UPDRS) will be performed by a Movement Disorder Specialist to assess the severity of Parkinson's disease.

- Timed Up and Go test (TUG) - a mobility test that is used to measure the basic mobility skills of people who are elderly or have neurological conditions such as PD and it includes a sit-to-stand component as well as walking 3m, turning and returning to the chair.
- Freezing of Gait Questionnaire (FOGQ) which is a self-report questionnaire consisting of 16 items regarding falls and walking problems.
- Gait analysis using wearable sensors (Mobility Lab) to measure the walking speed and step length.

If study subjects meet the eligibility criteria, they will be asked to sign the informed consent and asked to come to clinic for part 1 or for part 2 of the study without taking their Parkinson's medication for 12 hours.

Visit 1 Changes to the DBS stimulator will be done every 60 minutes for 4 hours in a random order.

- Bilateral stimulators ON, bilateral stimulators OFF, Right ON-Left OFF, Right OFF-Left ON.
- UPDRS scale
- Gait analysis using wearable sensors (Mobility Lab) to measure the walking speed and step length.

This visit will take about 5 hours. At the end of the visit study participants will go home with their initial settings.

PART 2

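### The Section 3 hypothesis concerns patients with freezing of gait, but entry requires only walking difficulty and no planned analysis separates freezers, although the FOGQ is collected at screening

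*Combined protocol and SAP*

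**What the plan says.** Section 3 contains the protocol's only directional hypothesis: "We hypothesize that in patients with FOG, unilateral stimulation on the most affected hemisphere will ameliorate walking in a higher degree than bilateral stimulation".

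Section 4 sets the gait requirement for entry: the patient "had developed difficulty walking 6-12 months after the DBS". No inclusion or exclusion criterion refers to freezing.

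Other statements of purpose are wider. The aim in Section 1 concerns "unilateral STN stimulation versus bilateral stimulation on gait kinematics in patients with PD and associated gait dysfunction". Section 3 opens with "In this study we aim to evaluate the effects of differential STN stimulation on walking". Section 5 says "This study is meant to see if there is improvement in gait or freezing of gait after changes in the stimulation parameters".

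Part 1 screening in Section 5 includes the "Freezing of Gait Questionnaire (FOGQ) which is a self-report questionnaire consisting of 16 items regarding falls and walking problems", along with the UPDRS and a neurological examination. No cut-off is given, and no eligibility or analysis rule uses the result. At Visit 1 every patient goes through all four settings: "Changes to the DBS stimulator will be done every 60 minutes for 4 hours in a random order".

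Section 7 plans summaries of centre and spread for demographics, velocity, stride length, TUG and UPDRS, plus adverse event frequencies. It names no freezer subset, does not list the FOGQ, and specifies no unilateral-versus-bilateral contrast.

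**The concern.** The group in the hypothesis is narrower than the group that will be enrolled, and nothing later in the plan brings them together. A patient with a slow, shuffling gait who has never frozen satisfies Section 4 and counts in the Section 7 summaries exactly as a freezer does.

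Two things are at stake. The first is interpretation: a pooled mean difference, large or small, is a statement about a mixture and cannot be read as a statement about freezers. This holds whatever the mix turns out to be, unless every enrolled patient happens to freeze. The second is size: if non-freezers gain less from unilateral stimulation than freezers do, the pooled difference understates the effect that the hypothesis is about. That second consequence is conditional.

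**Working it through.** **1. Does walking difficulty imply freezing in this protocol?** No. Section 2 begins "Freezing of gait (FOG) and walking difficulties represent perhaps the most difficult challenges", naming the two as separate items, and Section 5 again separates gait from freezing of gait. The Section 4 criterion therefore cannot be read as shorthand for FOG.

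**2. Which stated purposes does the enrolled group serve?**

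| Statement | Population or target | Matches Section 4 entry? |
|---|---|---|
| Section 1 aim | PD with gait dysfunction | Yes |
| Section 3, opening sentence | Walking | Yes |
| Section 5, purpose | Gait or freezing | Yes |
| Section 3 hypothesis | Patients with FOG | No, narrower than entry |

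Only the hypothesis is left without a matching group.

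**3. How large could dilution be?** The documents give no sample size, power, alpha, effect size or share of freezers, so there is no figure to reproduce. All inputs below are assumptions.

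Let f be the share of freezers, d the mean paired difference in freezers, and g the non-freezer effect as a fraction of d. The pooled mean is m × d, with m = f + (1 − f)g. With the SD of the paired difference held constant, the number of patients needed for the same ratio of effect to standard error is multiplied by 1/m².

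| f | g = 0 | g = 0.5 | g = 1 |
|---|---|---|---|
| 0.8 | m = 0.80; 1/0.64 = 1.6 | m = 0.90; 1/0.81 = 1.2 | 1 |
| 0.5 | m = 0.50; 1/0.25 = 4.0 | m = 0.75; 1/0.5625 = 1.8 | 1 |
| 0.3 | m = 0.30; 1/0.09 = 11.1 | m = 0.65; 1/0.4225 = 2.4 | 1 |

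To put this on an absolute scale, assume two-sided alpha 0.05, 80% power and a standardised paired effect of 0.5 in freezers:

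- All freezers: n = ((1.960 + 0.842)/0.5)² = 31.4, so 32.
- f = 0.5, g = 0: standardised effect 0.25, n = (2.802/0.25)² = 125.6, so 126. Power with 32 patients is Φ(0.25 × √32 − 1.960) = Φ(−0.546) = 29%.
- f = 0.5, g = 0.5: standardised effect 0.375, n = (2.802/0.375)² = 55.8, so 56. Power with 32 patients is 56%.
- g = 1: n stays at 32.

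**4. What does analysing freezers alone cost?** With N enrolled, the freezer contrast rests on fN patients, so its standard error is 1/√f times that of the whole group at equal SD: 1/√0.8 = 1.12, 1/√0.5 = 1.41 and 1/√0.3 = 1.83.

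**The case against.** The strongest reply is that the mixed group is what most of the protocol asks for. Three of the four statements of purpose in the table fit the entry criterion, and the Section 2 rationale also covers balance problems and postural instability, with FOG prominent but not alone. A reader might infer from the mismatch that the trial cannot meet its stated objective. The documents do not support that: the broader aim is served, and only the FOG hypothesis is not.

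A reader might also infer that the comparison is known to be diluted. The hypothesis predicts a benefit in freezers and is silent on non-freezers. No section claims that the effect is specific to freezers, and the mix is unknown. A reversal of sign would further require that non-freezers do worse under unilateral than bilateral stimulation, and nothing in the documents points to that.

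The contrast is also within-patient, so admitting non-freezers does not bias it for those enrolled. Since the FOGQ is collected, freezers could be picked out afterwards. This stands in part: the data will exist. What is missing is a rule. The FOGQ is described as covering falls and walking problems, no cut-off is given, and the sensors are described as measuring walking speed and step length. Who counts as a freezer is therefore open to choice once results are known.

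Finally, Section 7 plans no contrast at all, so an all-freezer sample would still leave the hypothesis untested. That is a separate and larger gap. It does not remove this one, because descriptive means also have to be reported for the right group.

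**Conclusion.** The concern holds in a limited form. The hypothesis names patients with FOG, while entry and analysis do not, so results reported as planned would describe a mixed group and leave the FOG hypothesis unaddressed. This part rests on the text alone.

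Dilution is possible but not established. In the illustration it runs from none, with equal response, to about an elevenfold increase in patients needed, with 30% freezers and no effect in the rest. The multipliers depend on f and g, which the documents do not give, and on a constant SD of the paired difference. They should not be quoted as properties of this trial.

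The change is worth making because it determines what Part 1 can conclude about its own hypothesis and uses data already being collected.

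**What to change.** Leave Section 4 as it is and add the following to Section 7 for Part 1:

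- Class each patient as freezer or non-freezer from the screening FOGQ, supported by the screening UPDRS and neurological examination. Write the definition down before any setting is tested; collecting the FOGQ is not enough without a stated rule.
- For the Section 3 hypothesis, report in freezers the within-patient difference between unilateral stimulation of the most affected hemisphere and bilateral stimulation. Each patient's most affected hemisphere, and so which single-side setting enters the contrast, should be recorded in advance as well.
- Report the same difference in non-freezers and in the whole group, separately, for the broader aim on gait dysfunction.

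The cost is a smaller set, and so less precision, for the freezer comparison, as in step 4 of the working. Recruitment is unaffected and no new procedure or visit is needed.

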5. MEASUREMENTS AND EVALUATION

This study is meant to see if there is improvement in gait or freezing of gait after changes in the stimulation parameters.

- In the first part of the study subjects (1 visit) will be randomly assigned to four different stimulation parameters: both stimulators ON, both stimulators off, right stimulator ON, left stimulator ON. We will assess participants' gait using clinical scales as well as wearable sensors attached to the body. Assessments will be done one hour after each change in the stimulation parameters.
- In the second part of the study that participants may be asked to participate in, changes in the frequency of stimulation and contact stimulation will be performed. Four different stimulation settings will be tested. In this part evaluations will be done.

PART 1

Screening: At this visit, the study investigator will discuss the details of the research study and the consent form with the study participant.

The following procedures will also be completed:

- Sign informed consent form.
- Collection of a complete medical history and a neurological exam.
- United Parkinson's disease rating scale (UPDRS) will be performed by a Movement Disorder Specialist to assess the severity of Parkinson's disease.

- Timed Up and Go test (TUG) - a mobility test that is used to measure the basic mobility skills of people who are elderly or have neurological conditions such as PD and it includes a sit-to-stand component as well as walking 3m, turning and returning to the chair.
- Freezing of Gait Questionnaire (FOGQ) which is a self-report questionnaire consisting of 16 items regarding falls and walking problems.
- Gait analysis using wearable sensors (Mobility Lab) to measure the walking speed and step length.

If study subjects meet the eligibility criteria, they will be asked to sign the informed consent and asked to come to clinic for part 1 or for part 2 of the study without taking their Parkinson's medication for 12 hours.

Visit 1 Changes to the DBS stimulator will be done every 60 minutes for 4 hours in a random order.

- Bilateral stimulators ON, bilateral stimulators OFF, Right ON-Left OFF, Right OFF-Left ON.
- UPDRS scale
- Gait analysis using wearable sensors (Mobility Lab) to measure the walking speed and step length.

This visit will take about 5 hours. At the end of the visit study participants will go home with their initial settings.

PART 2

Screening: At this visit, the study investigator will discuss the details of the research study.

The following procedures will be completed:

- United Parkinson's disease rating scale (UPDRS) will be performed by a Movement Disorder Specialist to assess the severity of their Parkinson's disease.

- Timed Up and Go test (TUG) - a mobility test that is used to measure the basic mobility skills of people who are elderly or have neurological conditions such as PD that includes a sit-to-stand component as well as walking 3m, turning and returning to the chair.
- Freezing of Gait Questionnaire (FOGQ) which is a self-report questionnaire consisting of 16 items regarding falls and walking problems.
- Gait analysis using wearable sensors (Mobility Lab) to measure the walking speed and step length.
- The PI will review the medical records to assess if precise localization of the electrode contacts can be done using the CT scan that was performed post-operatively and will decide if an MRI of the brain is necessary to perform.

Visits 1, 2, 3 and 4

During these visits the stimulation settings will be changed to one of the following conditions: Low frequency stimulation-dorsal STN, Low frequency stimulation- ventral STN, High frequency stimulation- dorsal STN, High frequency stimulation –ventral STN

After each change the following tests will be performed:

- United Parkinson's disease rating scale (UPDRS) will be performed by a Movement Disorder Specialist to assess the severity of Parkinson's disease.
- Timed Up and go test (TUG) - a mobility test that is used to measure the basic mobility skills of people who are elderly or have neurological conditions such as PD and it includes a sit-to-stand component as well as walking 3m, turning and returning to the chair.
- Freezing of Gait Questionnaire (FOGQ) which is a self-report questionnaire consisting of 16 items regarding falls and walking problems.
- Gait analysis using wearable sensors (Mobility Lab) to measure the walking speed and step length.
- Clinical Global Improvement Scale

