7. STATISTICAL ANALYSIS

For the data analysis, we will estimate frequencies of adverse events, central tendency and variability for patient's demographic characteristics, velocity, stride length, TUG and the UPDRS score. All analyses will be conducted using SAS (version 9.2, SAS Institute Inc., Cary, NC).

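### Part 1 states a random order of the four settings but no balancing over position or preceding setting, and the analysis has no period term, so drift over the visit can add chance error to the unilateral-bilateral contrast

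*Combined protocol and SAP*

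**What the plan says.** Section 5 states that in Part 1 "subjects (1 visit) will be randomly assigned to four different stimulation parameters". The Visit 1 list gives them as "Bilateral stimulators ON, bilateral stimulators OFF, Right ON-Left OFF, Right OFF-Left ON", so each patient serves as their own control over four periods in one visit. On timing and order it says "Changes to the DBS stimulator will be done every 60 minutes for 4 hours in a random order", and earlier in the section "Assessments will be done one hour after each change in the stimulation parameters". Patients attend "without taking their Parkinson's medication for 12 hours".

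No sequence list, blocking or method of generating the order is described, and no reason is given for the one-hour interval.

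For Part 2, Visits 1 to 4, the text is "During these visits the stimulation settings will be changed to one of the following conditions", with four combinations of frequency and contact location. Neither a fixed nor a random order is stated.

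The hypothesis in Section 3 is that "unilateral stimulation on the most affected hemisphere will ameliorate walking in a higher degree than bilateral stimulation". Section 7 plans to estimate "central tendency and variability for patient's demographic characteristics, velocity, stride length, TUG and the UPDRS score" and adverse event frequencies. It names no comparison of settings and no period, sequence or preceding-setting term. No sample size appears anywhere in the document.

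**The concern.** Part 1 is a four-period crossover in which time itself may matter. Patients arrive after 12 hours without medication, so time off medication lengthens from the first setting to the last. Fatigue over a visit of about five hours is also plausible, as is some remaining effect of the previous setting.

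Randomising the order protects against systematic bias from drift. It does not ensure that, in the patients actually enrolled, the bilateral and unilateral settings fall equally early or late, or follow the OFF setting equally often. With raw means and no period term, any such imbalance passes directly into the contrast that Section 3 is about. Once the visits are done the order cannot be rebalanced.

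**Working it through.** The plan gives no sample size, power or effect size, so there is no figure of its own to reproduce. The check asks how uneven the placement of two settings would be.

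**Inputs.** From Section 5: four settings, four periods, one period nominally one hour. Assumed: n = 8, 12, 20 and 40; each patient's order drawn independently from the 24 possible orders.

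**1. Position imbalance.** Let D be the period of a unilateral setting minus the period of the bilateral setting in one patient. Over the 24 orders, D = ±1 in 12, ±2 in 8 and ±3 in 4. Its mean is 0 and its variance is (12×1 + 8×4 + 4×9)/24 = 80/24 = 10/3. The mean of D over n patients therefore has SD = √(10/(3n)). The probabilities below come from the exact distribution of the sum of n such differences.

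| n (assumed) | SD, periods | P(more than half a period) | P(at least half a period) |
|---|---|---|---|
| 8 | 0.65 | 39% | 50% |
| 12 | 0.53 | 31% | 39% |
| 20 | 0.41 | 20% | 25% |
| 40 | 0.29 | 8% | 9% |

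**2. Effect on the contrast.** A linear drift of d units per hour adds an error with mean 0 and SD of 0.65d, 0.53d, 0.41d and 0.29d to the unadjusted difference. The documents give no value for d.

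**3. What a Williams square does.** With B = both on, R and L = one side on, the four sequences B-OFF-L-R, OFF-R-B-L, R-L-OFF-B and L-B-R-OFF place each setting once in each position, and all 12 ordered predecessor pairs occur exactly once. R minus B positions are 3, −1, −3, 1 and L minus B positions are 2, 1, −2, −1. Each set sums to 0, so linear drift cancels when n is a multiple of four.

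**4. The hypothesised contrast.** Section 3 compares the most affected hemisphere with bilateral stimulation, not right or left with bilateral. If the affected side varies 50:50 (assumed) and the square is coded right/left, each patient's value is one of the two figures for their sequence. The gaps between the two are 1, −2, −1, 2, so the variance is the mean of (gap/2)² = (0.25 + 1 + 0.25 + 1)/4 = 0.625. For this square the SD is √(0.625/n) = 0.28, 0.23 and 0.18 periods at n = 8, 12 and 20. Coding the square by most/least affected hemisphere makes it 0.

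**5. Carry-over.** Let a fraction λ of the preceding setting's effect persist, with the bilateral effect = 1, OFF = 0 and each unilateral effect = u. Both under independent random orders (on average) and in the square, each setting follows each other setting in 1/4 of patients. Expected carry-over into B is λ(0 + u + u)/4 and into R is λ(1 + 0 + u)/4. The bias in B minus R is λ(u − 1)/4 in both designs. With u = 0.5 (assumed) this is −0.125λ. The square removes only the chance part, whose SD at n = 12 is 0.157λ for u = 0.5.

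**6. Value of the square once period is fitted.** A period term removes additive drift under any order. By simulation, independent orders then cost on average about 18%, 10% and 6% in variance relative to the square at n = 8, 12 and 20.

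**The case against.** The strongest reply is that the protocol already randomises order, that the imbalance has expectation zero, and that a period term would deal with additive drift under any order, so the square is mainly a gain in efficiency. Most of this stands. The effect is noise and shrinks with the square root of n. But Section 7 plans no period term, so under the text as written the noise is not removed.

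Four stronger readings are tempting, and the documents do not support them:

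- **That the trial uses unrestricted randomisation in place of a balanced design.** The text does not say so. Random allocation of patients to Williams sequences would also fit it. The method is simply unspecified, and the figures above apply only if orders are drawn independently.
- **That the crossover is small.** No sample size is stated, which is why a range up to n = 40 is shown.
- **That there is no interval at all between settings.** Assessment comes one hour after each change, which acts as an equilibration period. Whether an hour is enough cannot be settled from these documents.
- **That a balanced square would dispose of carry-over.** It would not, as step 5 shows.

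It can also be said that the larger gap is the absence of any planned comparison of settings in Section 7. That is fair, and the fix below supplies one.

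**Conclusion.** The point holds as a cheap improvement to the design and analysis, not as a demonstrated bias. No balancing and no period term are stated for Part 1, and no order is stated for Part 2. A site following the text could draw orders independently and compare raw means. In that case two settings would differ in mean position by more than half a period with probability 39% at n = 8, falling to 8% at n = 40, and linear drift would enter the contrast in proportion.

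This rests on independent draws, the assumed sample sizes, and some drift over the visit; lengthening time off medication makes drift plausible, but the documents do not quantify it. The residual imbalance under right/left coding also rests on an assumed 50:50 split of affected side, and the carry-over figures on assumed u and λ.

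**What to change.** 1. In Section 5, Part 1, state that patients are randomised in blocks of four to the four sequences of a Williams square, with the unilateral settings coded as most and least affected hemisphere (or with randomisation stratified on the affected side). State how that hemisphere is identified and record it before allocation.
2. In Section 5, Part 2, assign the order of the four settings by a Williams square in the same way.
3. In Section 7, add a mixed model for each gait outcome with setting and period as fixed effects and patient as a random effect, and name the Section 3 contrast. Add a sensitivity analysis that includes the preceding setting, since balance alone leaves mean carry-over bias in place.

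The cost is a pre-printed sequence list and a few model terms. The Part 1 visit length and the number of settings do not change. Balance is exact only when the number of patients (per stratum, if stratified) is a multiple of four and all four periods are completed; otherwise the period term handles the small remainder.
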